3.7.2 Follow-up

Clinical and parasitological evaluation will be done on each day of follow-up or on any other day if the patient feels unwell. Patients will be reminded by phone calls 30minutes before the next dose of AL and on the day before the follow up visit (all enrollees i.e. PA and AL arms) and those who fail to attend follow up will be visited at home. Transportation fare will be given as incentives to the parents or care givers to encourage attendance for follow up. During each visit, a brief clinical history will be obtained to assess new complaints and possible side effects of medications and a physical examination will also be performed. Hematocrit and chemical analysis (bilirubin, blood glucose, creatinine and liver enzymes- AST, ALT & Alkaline Phosphatase) will be done on at enrolment and follow up on days 3, 7 and 28 to monitor possible changes.

Filter paper blood samples for parasite genotyping will be obtained on day 0, 3, 7, 14, 21 and 28 or earlier if enrollee is symptomatic. A finger prick blood sample will be taken to prepare thick blood smears on days 1, 2, 3, 7, 14, 21, 28 and on any other (unscheduled) visit. The slides will be air-dried away from direct sunlight, stained with fresh 10% Giemsa at pH 7.2 for 15 to 20 minutes and read independently by two microscopists. Parasite density (the number of asexual parasites per μl) will be calculated by counting parasites against about 200 leukocytes and assuming a leukocyte count of 8,000/ μl of blood ³⁶. A smear will be considered negative only after screening at least 200 high power fields. However, a slide will be read against 500 leukocytes before it is declared negative. All discordant smears and slides with a parasite density difference $>10\%$ will be read by an independent microscopist and the PI. For quality control 5% of randomly selected slides will be read by an independent microscopist not involved in the study.

Paired samples (D0 and Day of recurrence) of blood spots on filter paper collected from patients with parasite recurrence on or before D28 will be analyzed using PCR techniques for parasite DNA.

Enrollee will be withdrawn from the study if the parent/care giver withdraws consent, enrollee develop serious concomitant illness or report taking other unauthorized anti-malarial medication apart from the study drugs during the follow-up period. Those who withdraw consent will be revolved back to the hospital care while those who develop serious concomitant illness would have immediate medical care given to them and thereafter be referred for specialist care at Oni memorial children's hospital or University College Hospital, Ibadan at no cost to them. Enrollees who fail treatment with either of the two ACTs being evaluated will receive the alternative ACT under supervision.

Daily checks and corrections will be carried out on the CRF of enrollees seen to ensure correctness and accuracy. Blood samples collected from study participants will be transported to the respective laboratories in the University College Hospital Ibadan for analysis of blood chemistry and hematology parameters the same day they are collected. Efficacy parameters will be evaluated as follows:

- **Efficacy evaluation** will be based on WHO criteria of treatment outcome as follows; (1) Early treatment failure (ETF; danger signs or complicated malaria or failure to adequately respond to therapy on days 0–3); (2) Late clinical failure (LCF; danger signs or complicated malaria or fever and parasitemia on days 4–28 without previously meeting criteria for ETF or LPF); (3) Late parasitological failure (LPF; asymptomatic parasitemia on days 7–28 without previously meeting criteria for ETF or LCF); (4) Adequate clinical and parasitological response (ACPR; absence of parasitemia on day 28 without previously meeting criteria for ETF, LCF, or LPF).
- **Recrudescence** will be defined as the recurrence of asexual parasitemia within 28 days following antimalarial treatment comprising the same genotypes that caused the original illness. This is believed to result from incomplete clearance of asexual parasitemia because of inadequate or ineffective treatment.
- **Parasite clearance time**: time from first dose of ACT until first total and continued disappearance of asexual parasite forms.
- **Fever clearance time**: time from first dose until the first time the body temperature (for those with a raised temperature at enrolment) decrease to below 37.5°C and remain so for at least 24 hours.
- **Gametocyte carriage**: proportions of patients with gametocyte at a given point in time using the Area Under the Curve Graph for PA will be compared with that of AL.

3.7.3 Safety parameters will be evaluated as follows:

- Safety will be analyzed in terms of adverse events and severe adverse events using clinical signs, symptoms and laboratory parameters.
- Liver enzymes (ALT/AST) >3 times upper limit of normal (ULN) plus peak total bilirubin >2 times ULN in the absence of a significant alkaline phosphatase increase (= Hy's law) will be deemed as serious adverse effects (SAE).
- ALT and AST >5 times ULN will be deemed an AESI. (see below)

Serious Adverse Events

An adverse event will be considered serious if it fulfils one of the following criteria:

- causes death or
- is life-threatening or necessitates hospitalization or prolongs hospitalization or results in persistent or significant disability/incapacity or is a medically important event constitutes a possible Hy's Law

An example of an important medical event is one that while not-immediately life-threatening might become so if there had been no intervention

In case of SAEs, independent of causality, the healthcare personnel must immediately contact the PI / Investigator for validation of the seriousness and determination of the causality.

Subsequently, the procedure described below must be followed:

- SEND (within 24 hours and pdf scanned documents) the signed and dated copy of the “Adverse Event form” and the form “SAE complementary information” to Shin Poong Pharmacovigilance (PV) (Tel/[contact] or email: [contact])
- Contact immediately (the same day) the medical monitor/Pyramax QPPV responsible for safety in case of death or life-threatening events.
- The follow-up of each fatal or life-threatening AE must be provided to the medical monitor and Shin Poong PV within the same timeline as the initial report (within 24 hours and preferably by email).
- ATTACH to the Case Record Form (CRF) the photocopy of all available results and examinations which were undertaken (and their date). Analysis results must be accompanied by the laboratory normal ranges. Special consideration shall be taken to ensure patient anonymity, and to the correct completion of the patient’s study specific identifier in the copies of the source documents provided to the sponsor.

Causality

All adverse events must have causality assigned by the investigator. As a guide causality can be assigned as follows:

- Not related
 - The Investigator has determined that the adverse event is not related to the study medication
 - The current state of knowledge indicates that a relationship to the use of study medication is unlikely
- Related
 - The Investigator has determined that the event has a reasonable relationship to the use of the study medication
 - The Investigator has determined that the complication is more than likely related to the study medication

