3.6.2 Exclusion criteria

- History of allergy to study drugs i.e. artemisinins, lumefantrine and pyronaridine
- Any concurrent illness that could hamper evaluation of response e.g. bacterial infections, viral infections, severe gastrointestinal disease, malnutrition (weight for height $<70\%$)
- Presence of clinical evidence of severe malaria such as prostration, inability to drink or breast feed, persistent vomiting, convulsion, severe anemia hemoglobin <5 g/dl), unarousable coma
- Patients with known chronic diseases like chronic kidney disease, chronic liver disease, malnutrition, cardiac failure, Sickle Cell haemoglobin (HbSS) etc.
- mixed or mono-infection with another Plasmodium species detected by microscopy;
- presence of severe malnutrition defined as a child aged between 6-60 months whose weight-for-height is below -3 z-score, or has symmetrical edema involving at least the feet or has a mid-upper arm circumference <115 mm)
- Parent or guardian who in the judgment of the investigator will not comply with protocol in the opinion of the investigator

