3.7.1 Drug administration

Study participants will then be assigned into one of the two treatment groups according to a pre-generated randomization code. Drug treatment will be given in the clinic supervised.

Pyronaridine-artesunate:

Children randomized to group 1 will receive three doses of pyronaridine-artesunate granules or tablets (Pyramax®) manufactured by Shin Poong Pharmaceuticals depending on their body weights. Pyramax® granules comes in sachets with each containing 60mg of pyronaridine/20mg of artesunate while Pyramax tablets contain 180mg pyronaridine/60mg artesunate. Pyramax dosing is once daily for three days. Dosing will be according to the chart below:

| Body weight | No of sachets or Tablets | Regimen |
|--------------|--------------------------|------------------|
| 5 - < 8kg | 1 Sachet | Daily for 3 days |
| 8 - < 15Kg | 2 sachets | Daily for 3 days |
| 15 - < 20 Kg | 3 Sachets | Daily for 3 days |
| 20 - < 24 Kg | 1 Tablet | Daily for 3 days |
| 24 - <45 Kg | 2 Tablets | Daily for 3 days |

Artemether-lumefantrine:

The study participants randomized to group 2 will receive the standard six-dose regimen of artemether-lumefantrine dispersible tablets (Coartem® Novartis pharma) twice daily according to body weights. Each dispersible tablet of Coartem® contains 20mg of artemether/120mg of lumefantrine) and patient will be dosed as follows

| Body weight | No of dispersible Tablets |
|--------------------|----------------------------------|
| 5 -<15 Kg | 1 tablet |
| 15 - < 25 Kg | 2 tablets |
| 25 - <35 Kg | 3 Tablets |
| ≥35 Kg | 4 Tablets |

5 -<15Kg one tablet, 15 - <25 Kg two tablets, 25 - <35 Kg three tablets, and ≥35 Kg four tablets at the following dosing intervals

- 0 hour - 1st dose;
- 8 hours – 2nd dose;
- 24 hours – 3rd dose;
- 36 hours – 4th dose;
- 48 hours – 5th dose
- 60 hours – 6th dose.

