3.7.5 Follow-up of Adverse Events

The healthcare personnel must take all appropriate measures to protect the safety of the patients. Personnel must ensure to document follow-up of the evolution of each adverse event (clinical, biological or other) until resolution or until the stabilization of the patient's status.

All new relevant information concerning the initial SAE shall be recorded on a form "SAE follow-up information form" by the nursing staff of the health centre, and shall be validated by the PI/co-PI who shall transfer the form to the local person/physician responsible for the pharmacovigilance of the project and Shin Poong PV.

In case of a serious adverse event the patient must be followed until complete resolution and normalization of all analysis results, or until chronicity of the patient's status. This can imply that the follow-up of the patient must continue beyond the period of follow-up per protocol, and that additional investigations could be requested.

DATA ANALYSIS.

Data will be entered into the computer using the Epi-data software. This subsequently would be cleaned and transferred to SPSS Statistic Software version 20 for analysis. The outcome of interest (dependent variable) presented as a categorical variable with, presence of malarial parasitemia, and the level of efficacy reported. The independent or explanatory variable of interest in this study would be use of chemotherapy. All independent variable would be reported as categorical. Proportions of treatment outcome will be compared by using chi square. Normally distributed continuous data will be compared using unpaired student t-test. Mean values will be given as mean \pm SD and values of $P < 0.05$ will be considered statistically significant.

ETHICAL CONSIDERATIONS

This study, will be a prospective randomized open label clinical trial comparing the safety and efficacy of Pyronaridine-artesunate and Artemether-lumefantrine in the treatment of symptomatic acute uncomplicated malaria in Nigerian children aged 3 to 144 months who seek treatment in the study hospital. The studies will be conducted according to Good Clinical Practice and the Declaration of Helsinki.

Confidentiality of data: Personal details of enrollees in the study will be treated with utmost confidentiality, as it is against the principles of good clinical practice to make such information public. Also, codes will be assigned to all participants.

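### The rescue rule sends every treatment failure to the other oral ACT, including children who fail with danger signs or complicated malaria

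*Combined protocol and SAP*

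**What the plan says.** Section 3.7.2 (Follow-up) states the rescue rule in one sentence: "Enrollees who fail treatment with either of the two ACTs being evaluated will receive the alternative ACT under supervision". It makes no exception for the type or severity of failure.

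The efficacy definitions in the same section place severe disease inside two failure categories:

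- Early treatment failure, days 0 to 3: "ETF; danger signs or complicated malaria or failure to adequately respond to therapy".
- Late clinical failure, days 4 to 28: "LCF; danger signs or complicated malaria or fever and parasitemia".

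Section 3.7.1 (Drug administration) fixes the formulations. For PA: "Children randomized to group 1 will receive three doses of pyronaridine-artesunate granules or tablets". For AL, it is the "standard six-dose regimen of artemether-lumefantrine dispersible tablets".

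At entry the protocol is stricter. Section 3.6.1 requires that the child can take oral drugs. Section 3.6.2 excludes children with "Presence of clinical evidence of severe malaria such as prostration, inability to drink or breast feed, persistent vomiting, convulsion", and also those with severe anaemia or unarousable coma.

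**The concern.** A child who shows these signs on day 0 cannot be enrolled and given either study drug. If the same child is enrolled well and develops the signs on day 2 or day 10, the child is a treatment failure, and the rescue rule prescribes the other study drug by mouth. Not every child with a severe sign is unable to swallow, but some are, and the rule does not exempt them.

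The safety of the sickest failures is at stake, in a trial that enrols infants from 3 months of age. The fault lies in a positive treatment instruction, so it is more than missing detail. The concern does not claim any effect on an endpoint that has already been reached.

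**Working it through.** **Step 1: does the rule reach these children?** The rule covers enrollees who fail treatment. ETF and LCF are failures, and both definitions include danger signs or complicated malaria. So the rule reaches them.

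**Step 2: is the rescue drug oral?** The rescue sentence does not use the word. It follows from 3.7.1, where PA comes only as granules or tablets and AL only as dispersible tablets. Whichever drug the child started on, the alternative is oral.

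**Step 3: does any other text supply a different treatment?**

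| Place | What it covers | Does it qualify the rescue rule? |
|---|---|---|
| 3.7.2, referral clause | "those who develop serious concomitant illness would have immediate medical care given to them and thereafter be referred for specialist care" | No. It concerns concomitant illness as a reason for withdrawal; failures have their own sentence straight after it. |
| 3.7.3, serious adverse events | Seriousness criteria, contact with the investigator and medical monitor, reporting times | No. It names no treatment. |
| 3.7.5 | "The healthcare personnel must take all appropriate measures to protect the safety of the patients" | No. It is a general duty and names no treatment or pathway. |
| Ethical considerations, beneficence paragraph | Malaria and related febrile illness are treated free of charge | No. It settles cost, not treatment. |
| 3.7.1, repeat vomiting | The child is withdrawn and given another ACT | No. It escalates only to another ACT. |
| 3.7.1, other antimalarials | None for 28 days unless parasites recur | No. Read literally, it does not permit another antimalarial for an early failure without recurrence. |

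None of these gives a pathway for a child whose study malaria becomes complicated.

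**Step 4: how many children?** The protocol gives no rate for failures with danger signs, so only a range can be shown. Section 3.6 plans on 28-day cure rates of 96.4% (AL) and 98.9% (PA), with 84 per arm enrolled and 70 per arm before the allowance for loss.

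- Failures of all types at 84 per arm: 84 × 0.036 + 84 × 0.011 = 3.02 + 0.92 = 3.95 (from unrounded terms).
- At 70 per arm: 70 × 0.036 + 70 × 0.011 = 2.52 + 0.77 = 3.29.

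Only a subset would be affected. Late parasitological failure is asymptomatic by definition, and LCF can be fever with parasitaemia alone. Let *s* be the share of failures with danger signs or complicated malaria (assumed). At 84 per arm, the expected number is 3.95*s*, and the chance of at least one is 1 − (1 − 0.036*s*)^84 × (1 − 0.011*s*)^84.

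| *s* (assumed) | Expected children | Chance of at least one |
|---|---|---|
| 5% | 0.20 | 18% |
| 10% | 0.39 | 33% |
| 25% | 0.99 | 63% |
| 50% | 1.97 | 86% |

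Section 3.6 does not say whether its cure rates are corrected for reinfection, so it is unclear whether reinfections are in the count of 3.95.

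**The case against.** The best defence reads the protocol as a whole. Section 3.7.5 is itself protocol text and is mandatory. Complicated malaria that threatens life or needs admission is a serious adverse event under 3.7.3, so an investigator is contacted at once. The trial runs in a children's hospital that is one of the two referral centres named in 3.7.2. The rescue sentence sets no timing and does not forbid emergency care. On this view the fault is a drafting omission that any clinician would read past. The proposed change, which leaves drug and route to the investigators, adds little to the discretion they already have.

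Part of this stands. The setting makes harm less likely, and a clinician who departs from the rescue sentence can cite another part of the protocol for doing so. The assumed shares are not evidence of frequency, and a range from 18% to 86% cannot by itself support a severity rating. The consent pages and attachments were not available, so a pathway written there cannot be ruled out.

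The defence does not remove the conflict. A specific instruction names a treatment for all failures, and the general texts neither qualify it nor name another. Staff would have to put a general duty above a specific rule in an emergency.

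**Conclusion.** The concern holds. The rescue rule is unqualified, its scope includes children with danger signs or complicated malaria, both rescue drugs are oral, and the available text gives no other treatment pathway. This must be fixed because of how grave the harm to one child could be and how little the correction costs, not because many children are expected to be affected.

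The likely number is small: some fraction of about 4 failures at the planning rates, or 0.2 to 2.0 children if the affected share lies between 5% and 50%. That share is an assumption with no source in the protocol. The textual finding does not depend on it.

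**What to change.** 1. In 3.7.2, limit the alternative-ACT sentence to failures with none of the severe-malaria signs listed in 3.6.2.
2. Add one sentence to 3.7.2: failures with danger signs or complicated malaria receive immediate care and free referral, through Oni Memorial Children's Hospital or University College Hospital, for severe-malaria treatment, with drug and route set by the investigators. They are recorded as ETF or LCF, not as withdrawn. The recording clause matters because the existing referral text is written for withdrawn children, 3.7.2 also withdraws children who report unauthorised antimalarials, and the efficacy summary in the case record form codes withdrawal (5) separately from ETF (1) and LCF (3).
3. In 3.7.1, widen the exception to the bar on other antimalarials from parasite recurrence to any protocol-defined treatment failure, so that it plainly covers early failure without recurrence.

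The cost is two sentences and one phrase in an amendment. The hospitals and the free care are already in 3.7.2, and no visits, staff or patients are added.

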3 INVESTIGATION PLAN

3.1 Study Design

3.2 This is a randomized open label trial that will compare the safety and efficacy of PA and AL in patients of both sexes between the ages of 3 months and 10 years who have symptomatic microscopically confirmed acute uncomplicated *Plasmodium falciparum* malaria. Patients will be randomized following a pre-generated randomization code. On the basis of the results of these assessments, the patients will be classified as having therapeutic failure (early or late) or adequate clinical and parasitological response (ACPR). The proportion of patients experiencing therapeutic failure during the follow-up period will be used to estimate the efficacy of the study drug(s). The primary outcome will be PCR-adjusted adequate clinical and parasitological response (ACPR) i.e., absence of patent parasitaemia, regardless of axillary temperature and without evidence of previous treatment failure up to day 28. Secondary outcomes will be adequate clinical and parasitological response without correction for reinfection, parasite clearance time, fever clearance time and the proportions of patients who are aphasitaemic or afebrile on days 1, 2, and 3.

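### The early-failure rule sets no parasitaemia condition for danger signs, the late-failure rule is ambiguous on it, and neither is ranked against withdrawal for serious concomitant illness

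*Combined protocol and SAP*

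**What the plan says.** The efficacy evaluation in section 3.7.2 "will be based on WHO criteria of treatment outcome as follows", and the protocol then supplies its own wording:

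- Early treatment failure (ETF): "danger signs or complicated malaria or failure to adequately respond to therapy on days 0–3".
- Late clinical failure (LCF): "danger signs or complicated malaria or fever and parasitemia on days 4–28 without previously meeting criteria for ETF or LPF".
- Adequate clinical and parasitological response (ACPR): "absence of parasitemia on day 28 without previously meeting criteria for ETF, LCF, or LPF".

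The primary outcome, under Study Design, is PCR-adjusted ACPR, described as "absence of patent parasitaemia, regardless of axillary temperature and without evidence of previous treatment failure up to day 28". Genotyping is planned for "Paired samples (D0 and Day of recurrence) of blood spots on filter paper collected from patients with parasite recurrence on or before D28".

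Section 3.7.2 also withdraws a child if the "enrollee develop serious concomitant illness". The case record form gives the failure categories and withdrawal separate codes. The Data Analysis section compares outcome proportions by chi-square and does not mention withdrawn children.

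Danger signs are not defined for follow-up. The nearest list is a baseline exclusion in section 3.6.2: "Presence of clinical evidence of severe malaria such as prostration, inability to drink or breast feed, persistent vomiting, convulsion".

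**The concern.** The primary endpoint is meant to measure failure of the antimalarial. Signs such as persistent vomiting or convulsion also occur in other childhood illness. Consider a child whose smear is negative and who convulses on Day 2. Under the ETF wording this child is a treatment failure, which bars ACPR. Under the concomitant-illness rule the same child is withdrawn and has no failure code. Nothing says which rule wins, and the investigator making the call knows the arm. A child with the same signs on Day 10 raises the same question under LCF, on one of its two readings.

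Two things are at stake: dilution of the endpoint by non-malarial events in both arms, and, if calls differ by arm, bias in a comparison where very few true failures are expected.

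**Working it through.** **Reading the rules together**

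1. ETF has three alternatives joined by "or". None carries a parasitaemia condition.
2. In LCF the parasitaemia condition follows the fever term. It may qualify fever alone or all three terms. The text does not settle this.
3. Any earlier ETF or LCF bars ACPR, and so bars success on the primary endpoint, even if the Day 28 smear is negative.
4. Paired PCR is planned only for parasite recurrence, so it gives no route to reclassify a smear-negative failure.
5. Failure and withdrawal can both apply to one child. Neither section 3.7.2 nor the case record form ranks them.

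**Planning figure (section 3.6)**

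Inputs: cure rate P1 = 0.964 for AL and P2 = 0.989 for PA; margin 0.05; 90% power; 70 per group. The text refers to a one-sided 95% limit, so z = 1.645.

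n = (1.645 + 1.282)² × [0.964 × 0.036 + 0.989 × 0.011] / [0.05 − (0.964 − 0.989)]² = (2.927)² × 0.045583 / 0.075² = 69.4, which rounds up to 70.

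The plan's 70 is reproduced. (The listed deviate of 1.96 would give 86; that is a separate matter.)

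**Scale of one child**

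Expected failures per 70: AL 70 × 0.036 = 2.52; PA 70 × 0.011 = 0.77. One child is 1/70 = 1.43 points, or 29% of the 5-point margin.

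**Equal misclassification in both arms (assumed rates)**

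Let a share q of otherwise cured children be scored as failures, so that each cure rate is multiplied by (1 − q). With SE = √{[P1(1 − P1) + P2(1 − P2)]/70}:

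Power = Φ{[0.05 − (P1 − P2)]/SE − 1.645}

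| q | AL | PA | SE | Power | n per arm for 90% |
|---|---|---|---|---|---|
| 0 | 0.9640 | 0.9890 | 0.0255 | 90.2% | 70 |
| 0.5% | 0.9592 | 0.9841 | 0.0280 | 84.9% | 84 |
| 1% | 0.9544 | 0.9791 | 0.0302 | 79.6% | 99 |
| 2% | 0.9447 | 0.9692 | 0.0342 | 70.2% | 127 |

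At q = 1% this is about 0.7 extra failures per arm; at 2%, about 1.4.

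**Observed-count scenarios**

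One-sided 95% upper limit for AL minus PA cure, in points. The Wald limit is d + 1.645 × SE; the score limit is Miettinen–Nurminen. Non-inferiority holds if the limit is below 5.

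| Failures AL/PA, n = 70 | Wald | Score |
|---|---|---|
| 3/1 (start) | 1.76 | 2.38 |
| 4/2 (one more in each arm) | 2.76 | 3.33 |
| 5/3 (two more in each arm) | 3.58 | 4.10 |
| 6/4 (three more in each arm) | 4.29 | 4.75 |
| 3/2 (one more, PA only) | 3.73 | 4.57 |
| 3/3 (two more, PA only) | 5.63 | 6.56 |

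For 3/3 at n = 70: d = 0 and SE = √(2 × 0.0410/70) = 0.0342, so the limit is 1.645 × 0.0342 = 5.63 points. At the 84 per arm to be randomised, 3/3 gives 4.71 (Wald) and 5.52 (score), so there the verdict depends on the method.

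**The case against.** The protocol says its criteria rest on those of WHO, so parasitaemia may be intended and the text may be shorthand. That source is not available here, and site staff will apply the wording that is printed. If parasitaemia was intended, saying so costs nothing.

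The affected group is narrow, and this stands. Every child enrols with at least 1000 parasites/µl, so a smear-negative ETF needs clearance by Days 1 to 3 together with danger signs from another cause. Concurrent illness is excluded at baseline, though illness that arises during 28 days of follow-up is not.

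Three stronger readings are tempting, and the documents do not support them:

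- *That LCF definitely counts smear-negative children.* Its wording allows parasitaemia to govern all three terms. It is ambiguous, no more.
- *That a couple of such children would decide non-inferiority.* That requires the extra failures to fall on PA. Randomisation gives no reason to expect non-malarial illness in one arm only, and equal additions of one to three per arm keep the limit below 5 points by both methods. Open-label coding could make calls arm-specific, but nothing in the documents says that it will or how often.
- *That no blood sample would exist for PCR.* The activity table schedules filter-paper spots at every visit, extra visits included. The gap is that paired genotyping is planned only for recurrences.

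**Conclusion.** The concern holds in this limited form. The ETF gap is plain on the text, the LCF wording is ambiguous, and the missing precedence between failure and withdrawal leaves an outcome code open to choice by someone who knows the arm. The likely cost is lost power: about 90% falling to about 80% at an assumed 1%, and about 70% at an assumed 2%, equal in both arms. These rates are assumptions; the documents give none. A reversed verdict, such as 3/1 becoming 3/3 at 70 per arm, needs arm-specific classification and is an illustration of sensitivity, not an expectation.

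A reader might also infer that rewording the failure rules affects scoring alone. It may not: section 3.7.2 gives the alternative ACT to children who fail treatment, while section 3.7.1 permits other antimalarials only on parasite recurrence. For a smear-negative child scored as a failure, those two passages already conflict.

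**What to change.** In section 3.7.2, for scoring the efficacy endpoint:

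1. Require parasitaemia on the smear taken at that visit for the danger-sign and complicated-malaria limbs of both ETF and LCF. Keep the stated day windows: shifting ETF to start at Day 1 would drop from these limbs a parasitaemic child who deteriorates after dosing on Day 0.
2. Define danger signs for follow-up.
3. State that a smear-positive child who meets a failure limb is scored as a failure even if also withdrawn, and that a smear-negative child withdrawn for serious illness is not scored as a failure.
4. In Data Analysis, state how withdrawn children enter the primary analysis, and add a sensitivity analysis that counts them as failures.
5. Reconcile the section 3.7.2 rule on the alternative ACT after failure with the section 3.7.1 limit on other antimalarials. This review does not say which is right.

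The cost is a few lines of wording. No new procedure is needed, since smears are already planned at every scheduled and unscheduled visit. The downside is small: a few children become non-evaluable instead of failures in the primary analysis, which the sensitivity analysis makes visible.
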